8 EFFICACY ANALYSES

Missing efficacy data will be imputed as described in [Section 4.2.1](#) prior to reporting. As a sensitivity analysis, summaries will be repeated based on non-imputed (OC) data for the following variables:

- ASAS40 response relative to AS0008 Baseline at each visit in AS0009.
- ASAS20 response relative to AS0008 Baseline at each visit in AS0009.
- ASAS 5/6 response relative to AS0008 Baseline at each visit in AS0009.
- Change from AS0008 Baseline in BASDAI at each visit in AS0009.

A further sensitivity analysis will be performed for ASAS40 and ASAS20 response relative to AS0008 Baseline. The response endpoint will be re-derived and summarized based on the mean value (across multiple imputations) of the individual component scores after imputation for missing data.

Efficacy variables will be summarized and listed for the FAS. Summaries of MASES will be restricted to subjects with a MASES >0 at AS0008 Baseline. Maintenance of response summaries will be restricted to subjects who achieved a response at AS0008 Week 12 for the specific endpoint (where the response at AS0008 Week 12 is taken directly from the AS0008 datasets).

Responder variables (e.g. ASAS40 response) will be derived relative to the AS0008 Baseline and summarized using n and percentage at each visit, by treatment group at completion of AS0008 and overall.

Maintenance of response will be assessed for ASAS40, ASAS20 and ASAS5/6. The responses will be derived relative to AS0008 Baseline and summarized using n and percentage at each post-AS0008 Baseline visit, by treatment sequence across AS0008 and AS0009. These summaries will therefore include AS0008 Week 1, 2, 4, 8 12, 16, 24, and 36 and AS0009 EV (AS0008 Week 48), Week 12, 24, 36, 48, 60, 72, 84, 96, 108, 120, 132, 144, 156, 168, 180, 192, 204, and Week 208. AS0008 Week 1 and 2 are not applicable for ASAS5/6 response.

Absolute and change from AS0008 Baseline for all continuous efficacy variables will be summarized descriptively by visit, by treatment group at completion of AS0008 and overall.

Any data collected at the SFU visit will be excluded from all efficacy summaries; this data will be included in the listings only.

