13.8 Handling of dropouts or missing data

Missing binary efficacy variables will be imputed using nonresponder imputation (NRI). In NRI, each subject with missing data or who has prematurely finished the study will be counted as a nonresponder.

For missing continuous efficacy variables, a multiple imputation (MI) approach will be used. In MI, the missing value is replaced by a set of plausible values, where each value is a Bayesian draw from the conditional distribution of the missing data given the observed data.

Non-monotone missing data (ie, intermittent missing data) will be imputed several times with the Markov Chain Monte Carlo (MCMC) method and monotone missing data will be imputed using

a monotone regression model. Each set of imputed data will then be summarized and the summaries will be combined into a single inference (Carpenter and Kenward, 2013).

Safety data will not be imputed.

As a sensitivity analysis, all efficacy variables will be analyzed based on observed data. Subjects with missing data or who have prematurely finished the study will be treated as missing.

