 - For MASES the MI model will be restricted to subjects with a MASES score > 0 at AS0008 Baseline. Subjects with a MASES score of zero at AS0008 Baseline will be excluded prior to performing the procedure outlined below.
- PGADA
- TNSP
- SF-36
 - For SF-36 this will be performed for the Physical Component Summary score (PCS) and Mental Component Summary score (MCS) and for each of the 8 domain scores (Physical Functioning, Role Physical, General Health, Bodily Pain, Vitality, Social Functioning, Role Emotional and Mental Health).
- ASQoL
- HADS-A and HADS-D
 - Incidence of normal HADS-A and HADS-D scores (defined as having HADS-D<8 and HADS-A<8 at the same visit) will be derived at each visit using the values for HADS-A and HADS-D obtained after MI
- CRP
 - Note that for CRP as a standalone endpoint the rules for handling measurements that are below the limit of quantification should be followed as per [Section 8.1.12](#). Thus, if any

imputed values are <0.16mg/L these will be replaced with 0.08mg/L prior to any subsequent reporting.

The missing absolute value (not the change from baseline) will be replaced by one of a set of plausible values, where each value is a Bayesian draw from the conditional distribution of the missing data given the observed data. The basic assumption in MI is that the underlying missing data mechanism is ignorable, e.g. the missing data are missing at random.

All MI procedures will be performed using data from both AS0008 and AS0009 such that missing data across both studies will be imputed. Any previous MI or last observation carried forward (LOCF) (or other e.g., next observation carried backward) imputation performed in AS0008 will not be considered for AS0009 such that the procedure will use OC data only across both studies.

As the AS0008 Week 48 time point is synonymous with the AS0009 EV time point, this will be incorporated once only into the model.

The SAS® PROC MI procedure will be used for the imputation.

The MI consists of 3 steps:

- The missing data are imputed m times to create m complete datasets.
- The m datasets are summarized.
- The results of the m summaries are combined into a single result.

The MI method will be applied as follows:

Step 1

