^b For the purposes of the MI any numerical CRP values obtained in AS0009 that were <0.16mg/L will be substituted with half the lower limit of quantification (LLOQ) from AS0008 (ie, 0.08mg/L) prior to performing the MI. Subsequently any observed or imputed values of <2mg/L will be replaced by the value of 2mg/L for the purposes of deriving the ASDAS-CRP. Any CRP values of >=500mg/L will be set to missing prior to performing the MI procedure.

^c For the purposes of the MI any numerical CRP values obtained in AS0009 that were <0.16mg/L will be substituted with half the LLOQ from AS0008 (ie, 0.08mg/L) prior to performing the MI. Subsequently any imputed values of <0.16mg/L will be replaced by the value of 0.08mg/L for the purpose of summaries based on imputed data. Listings will display the original result. CRP values of >=500mg/L will be set to missing prior to performing the MI procedure; the subsequently imputed CRP value will be included in the summary tables.

Step 3 (Excluding CRP)

The 100 imputed datasets will be combined, and simple means and standard errors will be calculated using Rubin’s rules (via SAS® PROC MIANALYZE). For calculation of other

descriptive statistics (median, Q1, Q3, minimum and maximum), Rubin's rules do not apply. Multiple imputation estimates will be computed by calculating arithmetic means of the estimates from the multiple repetitions of the imputation algorithm. Thus, for median, Q1, Q3, minimum and maximum the following approach will apply:

- The data will be summarized by treatment, visit and imputation and the summary statistics will be computed.
- Results will be summarized by taking the mean value of each summary statistic at each visit across all imputations.

The number of decimal places will remain the same as the original for display purposes (ie, if the mean was presented to 1 decimal place, the mean of the means will also be presented to 1 decimal place).

Step 3 (CRP only)

The CRP data will be presented using the geometric mean, 95% confidence interval (CI) for the geometric mean, median, Q1, Q3, minimum and maximum. The change from Baseline will be expressed as the ratio to Baseline in the summaries. The following approach will be applied:

- Following the MI procedure the ratio to Baseline will be calculated for any of the imputed values
- The natural logarithm of the absolute values and of the ratios to Baseline will be calculated
- The logged values will be summarized by treatment, visit and imputation

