- The datasets will be combined using PROC MIANALYZE in order to get the mean and 95% CI estimates from the absolute values and ratios to Baseline (based on logged data) across imputations
- The estimates of the mean and 95% CI will be back-transformed to obtain the geometric mean and 95% CI on the original scale
- For the median, Q1, Q3, minimum and maximum the procedure outlined above for the other endpoints will be followed

As a sensitivity analysis, certain efficacy variables will be summarized based on observed data (see [Section 8](#)).

As a further sensitivity analysis for ASAS40 and ASAS20 responses, the response variables will be derived following MI of the individual components. The ASAS responses will then be derived for each subject and each imputation (where each imputation is performed across all individual components) and the number and percentage of subjects with each ASAS response in each imputation will be calculated. The mean value (across imputations) for the percentage of subjects with each ASAS response will be reported. Further details regarding data handling for the derivation of the ASAS response are provided in [Section 8.1.1.1](#) and will be implemented accordingly.

A similar approach will be followed for the calculation and summary of the number and percentage of subjects with normal HADS scores (defined as having HADS-D<8 and HADS-A<8 at the same visit) based on the HADS-D and HADS-A values after MI.

Primary and sensitivity analyses are summarized in **Table 4–2**. All summaries presenting data following MI will include only visits from AS0009 EV onwards (although the MI procedure will incorporate data from both AS0008 and AS0009).

Table 4–2: Missing data handling

Variable	Type	Missing data handling approach		
		NRI	MI/MCMC (monotone regression)	OC
ASAS40, 20	Responder	P	S ^a	S
ASAS component score (Total Spinal Pain [Question 1 from TNSP])	Continuous		P	
ASAS component score (Morning stiffness [the mean of BASDAI Questions 5 and 6])	Continuous		P	
ASAS5/6	Responder	P		S
BASDAI	Continuous		P	S
ASAS-PR	Responder	P		S
ASDAS-CRP	Continuous		P ^b	
ASDAS-CRP component score (Total Back Pain [Question 2 from the BASDAI])	Continuous		P	
ASDAS-CRP component score (Duration of Morning Stiffness [Question 6 from the BASDAI])	Continuous		P	
ASDAS-CRP (Peripheral Pain/Swelling [Question 3 from the BASDAI])	Continuous		P	
ASDAS-CRP (CRP ^c)	Continuous		P	

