ASDAS-ID (including Moderate, High and Very High Disease Activity Categories)	Responder		P ^a	
BASFI	Continuous		P	
BASMI	Continuous		P	
MASES	Continuous		P	
PGADA	Continuous		P	
TNSP	Continuous		P	
SF-36 PCS, MCS and domain scores	Continuous		P	

Table 4–2: Missing data handling

ASQoL	Continuous		P	
HADS-A, HADS-D	Continuous		P	
Incidence of normal depression/anxiety status (using HADS)	Responder		P ^a	
CRP ^d	Continuous		P	

ASAS=Assessment in SpondyloArthritis International Society; ASAS-PR= Assessment in SpondyloArthritis International Society Partial Remission; ASDAS-CRP=Ankylosing Spondylitis Disease Activity Score-C-reactive protein; ASDAS-ID=Ankylosing Spondylitis Disease Activity Score-Inactive Disease; ASQoL=Ankylosing Spondylitis Quality of Life; BASDAI=Bath Ankylosing Spondylitis Disease Activity Index; BASFI=Bath Ankylosing Spondylitis Functional Index; BASMI= Bath Ankylosing Spondylitis Metrology Index; CRP=high sensitivity C-reactive protein; HADS-A=Hospital Anxiety and Depression Scale – Anxiety; HADS-D=Hospital Anxiety and Depression Scale – Depression; MASES=Maastricht Ankylosing Spondylitis Enthesitis Index; P=primary method; PGADA=Patient’s Global Assessment of Disease Activity; S=sensitivity method; SF-36 MCS=Short Form 36-Item – Mental Component Summary; SF-36 PCS=Short Form 36-Item – Physical Component Summary; TNSP=Total Nocturnal and Spinal Pain.

^a Imputation method is applied on continuous data, and responder variable is derived from the continuous data based on complete dataset.

^b Imputation for ASDAS-CRP overall score is based on the MI of the individual components of the ASDAS-CRP with subsequent recalculation of the overall ASDAS-CRP based on each imputation in turn; for each subject the mean of the ASDAS-CRP scores will be used in the summaries. Direct MI of the ASDAS-CRP overall score is not performed.

^c Refers to imputation of CRP for the purposes of calculating the ASDAS-CRP.

^d Refers to imputation of CRP for the summaries of CRP as a standalone endpoint.

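### Two SAP sentences average imputed values within a subject and conflict with the SAP's own pooling rules: Section 8 for the ASAS40/ASAS20 MI sensitivity analysis, and Table 4-2 footnote b for ASDAS-CRP

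*SAP*

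**What the plan says.** **ASAS40/ASAS20, MI sensitivity analysis.** SAP Section 4.2.1 sets out a full procedure after imputation of the components: "The ASAS responses will then be derived for each subject and each imputation (where each imputation is performed across all individual components"). It then takes the percentage in each imputation and closes with "The mean value (across imputations) for the percentage of subjects with each ASAS response will be reported". SAP Section 8 describes the same analysis as response re-derived "based on the mean value (across multiple imputations) of the individual component scores after imputation for missing data". Section 8 also opens with "Missing efficacy data will be imputed as described in" and a reference to Section 4.2.1. Sections 8.2 and 8.3 say only that response is derived after MI of the components.

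**ASDAS-CRP.** Footnote b of SAP Table 4-2 imputes the components and recalculates the score in each imputation, and then says "for each subject the mean of the ASDAS-CRP scores will be used in the summaries". The general rules differ:

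- Protocol 13.8: "Each set of imputed data will then be summarized and the summaries will be combined into a single inference".
- SAP 4.2.1, third of the three MI steps: "The results of the m summaries are combined into a single result".
- SAP 4.2.1, Step 3, which exempts only standalone CRP: "The 100 imputed datasets will be combined, and simple means and standard errors will be calculated using" Rubin's rules. The median, quartiles, minimum and maximum are computed per imputation and then averaged.

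**The concern.** In both places the imputed values are collapsed to one number per subject before the summary is computed, which discards the variation that MI is meant to carry.

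For ASAS this matters because response is a threshold rule, and the response of an averaged score is not the average of the responses. This is the only MI check on the primary non-responder result for two of the three secondary efficacy variables, and two sections instruct the programmer differently.

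For ASDAS-CRP, MI is the only planned way of handling missing data, so the displayed spread rests on it. Within-subject averaging departs from Protocol 13.8, yet it is not among the changes to protocol-defined analyses listed in SAP 3.10. It also treats the score differently from its own activity categories, which SAP 4.2.1 counts within each imputation.

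**Working it through.** The plan gives no figure to reproduce: it is descriptive and states no missing rate, predictive strength (R²) or correlation between components. All sizes below are illustrations on stated assumptions.

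**1. ASAS: why the order matters.** From SAP 8.1.1, ASAS40 needs at least 40% and at least 2 units of improvement in three of four domains, with no worsening in the fourth. Take a subject with baseline 6 in every domain. The requirement is 0.40 × 6 = 2.4 units, so a score of 3.6 or less. Assume an imputed SD of 1.5 and a correlation of 0.6 between components.

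| Imputed mean | Share of imputations with response (4.2.1) | Response from averaged scores (Section 8) |
|---|---|---|
| 3.2 | 0.54 | 1 |
| 4.0 | 0.30 | 0 |

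Averaging first pushes subjects near the cut-off to a definite yes or no, so the direction of the error depends on which side most imputed subjects lie.

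**2. ASAS: size and direction.** Simulated with 100 imputations, values clipped to 0–10 and all four components missing together. Assumptions: baseline mean 6.5, SD 1.7; follow-up mean 2 to 5, SD 1.8 to 2.8; R² 0.3 to 0.8; component correlation 0.4 to 0.8; imputed residuals either correlated or independent. Overall shift = missing fraction × shift in imputed subjects.

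- ASAS40: the shift in imputed subjects runs from −11.4 to +21.9 points. At 30% missing this is 0.3 × (−11.4) = −3.4 to 0.3 × 21.9 = +6.6 points overall.
- ASAS20: the largest rise is +21.5 points, or 0.3 × 21.5 = +6.5 overall. At baseline 6.5 the ASAS20 cut-off is 6.5 − 0.20 × 6.5 = 5.2, so follow-up means of 5 or less nearly always give a rise. At a follow-up mean of 6 with correlated residuals, ASAS20 falls by up to about 7 points in imputed subjects, or 0.3 × 7 ≈ 2 points overall.
- At 10% missing and R² 0.6, the overall shift is about 1 point or less for either endpoint.

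One worked case with 285 subjects, 30% missing, follow-up mean 2.5 and conditional SD 2.0: ASAS40 is 63.2% by the 4.2.1 rule and 66.3% from averaged components, a difference of +3.1 points.

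**3. ASDAS-CRP: mean.** Averaging over imputations and then subjects equals averaging over subjects and then imputations, so the mean is identical.

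**4. ASDAS-CRP: spread.** Let f be the share missing. Observed scores keep variance σ². Scores averaged over many imputations have variance of about R²σ². The SD under footnote b, relative to the average per-imputation SD, is therefore √((1 − f) + f·R²) = √(1 − f(1 − R²)).

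- f = 0.10, R² = 0.8: √0.98 = 0.990, so 1.0% too small.
- f = 0.30, R² = 0.3: √0.79 = 0.889, so 11.1% too small. Simulation gave 11.0%.

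For the other statistics, simulated trials (250 subjects, assumed mean 2.0, SD 1.0, same f and R² ranges) were compared with Step 3. The maximum is 0.03 to 0.13 too low, any interquartile range is 1% to 20% too narrow, and the median is within 0.01.

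**5. ASDAS-CRP: standard error.** Rubin's variance is W + (1 + 1/100)·B, where W is the average within-imputation variance and B the variance between imputations. With one value per subject there are no separate imputation results from which to estimate B, so the standard error named in Step 3 cannot be computed.

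**6. SD.** SAP Table 3-1 plans an SD for ASDAS-CRP, but Step 3 names no pooling rule for it. Removing the footnote clause alone would leave the SD undefined.

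**The case against.** The best defence on ASAS is that Section 8 is one loose sentence. It refers to Section 4.2.1 for imputation, 4.2.1 gives the complete rule, and nothing else in the SAP calls for averaged components. That stands as far as it goes: the documents do not show that averaged components were ever used. But the reference covers how data are imputed, and the later sentence states its own derivation, which a programmer could follow.

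On ASDAS-CRP, footnote b can be read as a deliberate endpoint-specific exception. The SAP gives no reason for one and does not list it in 3.10. It is fair that the statistics planned in SAP 3.1 and Table 3-1 (mean, SD, median, minimum, maximum) include no quartiles or standard error, so the practical effect there is on the maximum and SD. The SD comparison uses the average per-imputation SD, which the SAP does not name, so for SD there is a gap rather than a direct contradiction.

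The sizes are assumed. The ASAS questionnaires can be collected remotely (SAP 5.1.1), so all four components need not be missing together. At remote visits CRP is the only ASDAS-CRP input necessarily missing. With assumed CRP predictability, the SD shortfall there is about 0.4% to 3.6%.

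**Conclusion.** Both conflicts are in the current SAP text and should be reconciled. Severity is minor: the study is descriptive, no decision rule depends on these tables, and the non-responder, observed-case and ASDAS category results are unaffected.

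A reader might infer that the ASAS MI rates are biased. The documents support only a conditional statement: they are biased if the Section 8 sentence is what was programmed. A reader might also infer that averaging first inflates the rates, with any fall confined to ASAS40. That does not hold. The sign depends on where imputed scores sit relative to the cut-off, and both endpoints can fall. The protocol lets investigators withdraw non-responders (Sections 5.1 and 7.8.1), so poor imputed scores cannot be ruled out. The size cannot be set from the documents.

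For ASDAS-CRP the direction is clear: the mean is unchanged, the median nearly so, and the spread is too narrow. The 1% to 11% SD shortfall rests on 10% to 30% missing and R² between 0.3 and 0.8.

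**What to change.** 1. SAP Section 8: replace the sentence with the 4.2.1 rule, that is, derive ASAS40 and ASAS20 in each of the 100 imputations and report the mean percentage.
2. SAP Table 4-2, footnote b: replace the last clause with wording such as: ASDAS-CRP is summarised within each imputation and pooled per Step 3.
3. SAP 4.2.1, Step 3, as a consequential edit: state how SD is obtained, for example computed per imputation and averaged.

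The cost is three sentences, since the procedure already creates the imputed datasets. The Week 108 interim (SAP 4.3) covered all outputs except those on COVID-19. The sponsor should therefore check which rule was programmed for the ASAS MI and ASDAS-CRP tables, and rerun only those built on averaged scores.

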8.1 Derivation of efficacy variables

Derived efficacy variables at AS0008 Baseline will be taken from the AS0008 database. Derivations described below will only be performed for data in the AS0009 database (which includes AS0008 Week 48 re-labelled as AS0009 EV).

For composite endpoints, component assessments will be combined based on the visit assignment following any mapping as described in [Section 3.5](#). Assessments from the same assigned visit will be used, regardless of actual assessment date.

8.1.1 Assessment in Axial Spondyloarthritis International Society Response Criteria

The ASAS20 response is defined as an improvement (decrease) of at least 20% and absolute improvement of at least 1 unit on a 0 to 10 numeric rating scale (NRS) in at least 3 of the 4 following domains (Anderson, 2001):

- PGADA
- Pain assessment (total spinal pain, question 1 from total and nocturnal spinal pain questionnaire)
- Function (represented by the BASFI)
- Inflammation (the mean of the BASDAI questions 5 and 6, concerning morning stiffness, intensity and duration)

This must be accompanied by the absence of deterioration in the potential remaining domain. Deterioration is defined as a relative worsening of at least 20% and an absolute worsening of at least 1 unit.

The ASAS criteria for 40% improvement are defined as relative improvement of at least 40% and absolute improvement of at least 2 units on a 0 to 10 NRS in at least 3 of the 4 domains and no worsening at all in the remaining domain (where worsening is defined as any worsening at all relative to baseline).

The comparison of changes to the specified cut-offs (i.e., ≥ 1 or ≥ 2 units) will be based on non-rounded data.

The ASAS 5/6 response is defined as at least 20% improvement in 5 of 6 domains, which includes, in addition to the 4 domains above, spinal mobility (lateral spinal flexion as recorded for BASMI) and CRP as more objective measures (Brandt et al, 2004). In the calculation of the ASAS 5/6 response the actual assessment value for the lateral spinal flexion will be used and not the transformed value used in the calculation of the BASMI score.

If the CRP value is below the lower limit of quantification (LLOQ) defined in AS0008 then it will be set to half of the LLOQ (as described in [Section 8.1.12](#)).

The ASAS partial remission (ASAS-PR) response is defined as a score of ≤ 2 units on a 0 to 10 unit scale in all 4 domains listed above.

